Study Protocol

Inhaled Nitrous Oxide for Treatment-Resistant Depression: Optimizing Dosing Strategies

Protocol Version:

6

5/24/2019

Principal Investigator:

[name] PhD
Assistant Professor of Anesthesiology
Department of Anesthesiology, [name]
[contact]
Email: [contact]

Co-Investigator:

[name], MSc
Professor of Anesthesiology
Department of Anesthesiology & Critical Care,
University of Chicago
Email: [contact]

[name]
Professor of Psychiatry
Department of Psychiatry, [name]
[contact]
Email: [contact]

ABSTRACT

Most clinical major depression responds to standard treatments (medication and psychotherapy); however, a significant subset of depressed patients (15-20%) do not respond to these treatments and are referred to as treatment-resistant major depression (TRMD). New treatments for TRMD are needed, and one promising line of research are drugs known as N-methyl-D-aspartate (NMDA) glutamate receptor antagonists. In a recent pilot study, our group demonstrated that the NMDA antagonist nitrous oxide (N_2O) is effective in TRMD, however, the dose concentration of nitrous oxide to have antidepressant effects is unknown. Therefore, we propose conducting a randomized, placebo controlled double-blind crossover (x2) study in which treatment-resistant depression patients will all receive 3 randomized, one hour nitrous oxide inhalation sessions of placebo (0% N_2O), 25% N_2O (low dose), and 50% N_2O (high dose). We aim to compare nitrous oxide's relative antidepressant efficacy of two doses of N_2O by demonstrating that inhaled nitrous oxide, but not inhaled placebo, will significantly show rapid and sustained antidepressant effects.

SYNOPSIS

Study Title	Inhaled Nitrous Oxide for Treatment-Resistant Depression: Optimizing Dosing Strategies
Objective	This study aims to determine whether different concentrations of nitrous oxide (N ₂ O) have different antidepressant effects for adults with treatment-resistant major depression.
Study Period	Planned enrollment duration: Approximately 2 years Planned study duration: Approximately 18 weeks
Number of Patients	40
Study Drug	Nitrous oxide (laughing gas). This is an FDA-approved general anesthetic and sedative agent used in hospitals and dentist offices. The use of nitrous oxide in this protocol is off-label and outside of the approved indication. Nitrous oxide will be administered under supervision of an attending-level anesthesiologist and using standard anesthesia equipment (mobile anesthesia machine/FDA-approved nitrous oxide delivery system, standard monitoring, oxygen, rescue equipment).
Study Design	Prospective, randomized, placebo-controlled, cross-over (x2) trial. All patients will receive 3 randomized, one hour N ₂ O inhalations to placebo (0% N ₂ O), low dose (25% N ₂ O), and high dose (50% N ₂ O). Inhalation sessions will be at least 4 weeks apart. Mood will be assessed at baseline, 24 hours, and 1, 2, and 4 weeks post-inhalation for each dose.
Inclusion and Exclusion Criteria	
Inclusion Criteria
 
 a) Adults 18-75 years of age; b) Current diagnosis of unipolar major depressive disorder (MDD) without psychosis as confirmed by structured clinical interview for DSM-IV disorders; c) A score of ≥ 9 on the Montgomery-Åsberg Depression Rating Scale (MADRS); d) Documented (i.e., chart review) lifetime failure to respond to ≥ 3 adequate dose/duration antidepressant treatment trials, ≥ 1 medication failure in the current depressive episode; e) Good command of the English language. 
Exclusion Criteria
 
 a) Meets criteria for any DSM-IV diagnosis for schizophrenia, bipolar, schizoaffective, obsessive-compulsive, personality, or panic disorders; b) Any recent (within past 12 months) history of substance dependence or abuse (except tobacco), determined by reported history and urine drug screen; c) Ability to become pregnant and not using effective contraception; d) Contraindication against the use of nitrous oxide: 
 1) Pneumothorax 2) Bowel obstruction 3) Middle ear occlusion 4) Elevated intracranial pressure 5) Chronic cobalamin and/or folate deficiency treated with folic acid or vitamin B12 6) Pregnant patients 7) Breastfeeding women e) Inability to provide informed consent; f) Any other factor that in the investigators' judgment may affect patient safety or compliance
Primary Outcome	Comparison of change in Hamilton Depression Rating Scale score at immediate (2 hrs) and sustained (24hrs) post nitrous oxide inhalation. Secondary depression measures will be assessed at the later time points for duration of sustained antidepressant effects.
Measurements	Hamilton Depression Rating Scale, HDRS-21 scale; Montgomery-Åsberg Depression Rating Scale, MADRS; Quick Inventory of Depressive Symptomology-Self Report, QIDS-SR; Clinician Administered Dissociative States Scale, CADSS-28 item; Brief Psychiatric Rating Scale, BPRS; Profile of Mood States, POMS-2, MINI International Neuropsychiatric Interview. Electroencephalography (EEG) during eyes open and eyes closed periods.
Statistical Methodology	Outcomes will be analyzed with a repeated measures mixed effects linear model using restricted maximum likelihood estimation. To adjust for the observed carryover effect, the model will include a randomization group term and a three-way interaction. Response and remission rates will be compared with an exact binomial test (and corresponding odds ratios calculated).

1. Specific Aims

- 1.1. To demonstrate that both low and high concentrations of nitrous oxide will show equivalent and superior antidepressant effects relative to placebo at immediate (2 hours) and sustained (24 hours) time points.
- 1.2. To compare the sustained antidepressant effect of low and high concentrations of inhaled nitrous oxide at 1, 2, and 4 weeks post-inhalation. We hypothesize that for both low and high doses, antidepressant effects will be attenuated at 1 and 2 weeks, and will dissipate by one month.

2. Background

It is estimated that as many as 16 million Americans suffer from major depressive disorder (MDD). Fifty percent fail an initial pharmacotherapy trial and ~30% fail a series of treatment trials [1], and are referred to as “Treatment-Resistant Major Depression” (TRMD). TRMD exacts a high toll on treatment resources and studies suggest that patients with TRMD place an unusually heavy burden on total MDD costs (suicide, personal financial costs, loss of work, medical co-morbidity [2, 3]). Unfortunately, knowledge regarding the best treatments for TRMD remains incomplete.

Studies demonstrate that there are limited effective antidepressant treatments for TRMD. Evidence shows that only four treatment approaches are effective in MDD after two sequential ineffective antidepressant trials: lithium augmentation, monoamine oxidase inhibitors, electroconvulsive therapy, and atypical antipsychotics (e.g. aripiprazole, quetiapine; [3]). To address this problem, the NIMH sponsored the largest sequential antidepressant trial (STAR*D). Following four levels of adequate dose-duration medications, ~36% of patients failed to remit [1]. *The STAR*D trial concluded that a significant proportion of MDD patients do NOT achieve remission and constitute TRMD.* With few exceptions, the majority of existing antidepressant treatments act via mechanisms discovered over three decades ago. ***Hence, antidepressant treatments with alternate mechanisms of action are needed.***

Over the past 15 years, multiple studies have indicated that the NMDA antagonist ketamine is an effective, rapid onset antidepressant in TRMD [4]. Most noteworthy, these studies suggest that ketamine acts immediately, producing an antidepressant response in less than 24 hours- a distinct advantage to existing antidepressant medications, which typically take 4-6 weeks to effectively decrease depressive symptoms. Despite the enormous potential benefits of ketamine in TRMD, this compound carries significant limitations: it is associated with psychosis, high addiction potential, and potential cognitive impairment [5-8].

Nitrous oxide (N₂O), an odorless, colorless gas typically used in anesthesia and dentistry, is an NMDA receptor antagonist [9]. Our group recently completed the first study of N₂O in TRMD patients [10]. Using a double-

blind, crossover design, we found that TRMD patients receiving a one hour session of inhaled N₂O (50% N₂O in 50% oxygen) versus placebo (50% nitrogen in 50% oxygen) experienced a significant decrease in MDD symptoms at 2 and 24 hours after inhalation, using the Hamilton Rating Scale for Depression-21 item (HDRS-21). Mean HDRS score differences at 2 hours: -4.8 points, $p=0.002$; and 24 hours: -5.5 points, $p<0.001$). Four patients (20%) had treatment response (HDRS reduction $\geq 50\%$) and three patients (15%) a full remission (HDRS ≤ 7 points) after N₂O, compared to one patient (5%) and none after placebo (odds ratio [OR] for response 4.0, 95% CI 0.45–35.8; OR for remission 3.0, 95% CI 0.31– 28.8). No serious adverse events occurred; however, *two patients experienced panic attacks/anxiety onset, suggesting that the inspiratory N₂O concentration may have been too high*. Importantly, the N₂O dose in our pilot study (50% N₂O in 50% oxygen) was based on its use in dentistry because no prior information about N₂O in TRMD existed.

Preclinical studies suggest that different doses of ketamine are associated with variable NMDA receptor and antidepressant activity. In single neurons, 50% N₂O blocks >50% of NMDA receptors, whereas ketamine concentrations achieved in depression studies likely block ~25-35% of NMDA responses [11]. Thus, it is possible that a lower inspiratory concentration of N₂O (25%) will have substantial antidepressant effect while also reducing the risk of paradoxical anxiety.

We propose a pilot study using a double-blind, crossover (x 2), placebo-controlled design to determine whether different concentrations of N₂O have different antidepressant effects. We hypothesize that 25% and 50% N₂O, as compared to placebo, will have equivalent antidepressant effects. Further, we predict that these effects will occur rapidly (2 hours) and be sustained (24 hours, one and two weeks), but will attenuate by one month.

3. Drug Information

Nitrous oxide (laughing gas) is a colorless, odorless gas. Nitrous oxide is the oldest and most widely used FDA-approved anesthetic gas. It is commonly used as a component of general anesthesia and as a sedative/analgesic agent used in hospitals and dentist offices. The onset as well as offset of effect is within a few minutes. Nitrous oxide is the least potent of inhalational anesthetics. Concentrations above 1 atm are theoretically needed to produce complete general anesthesia when nitrous oxide is used as a sole agent. Therefore, concentrations typically used (50%) in dentistry and pediatrics achieve only mild to moderate sedation (but potent analgesia) and are not sufficient to produce general anesthesia. Well-known side effects include euphoria, sedation, nausea and vomiting, inactivation of vitamin B₁₂ (commensurate with the duration of exposure and concentration used). In general, exposure to 25-50% nitrous oxide for 1 hour is considered extremely safe. The use of nitrous oxide in this protocol is off-label and outside of the approved indication.

4. Eligibility

4.1. Inclusion Criteria

- a) Adults 18-75 years of age;
- b) Current diagnosis of unipolar major depressive disorder (MDD) without psychosis as confirmed by structured clinical interview for DSM-IV disorders;
- c) A score of ≥ 9 on the Montgomery-Åsberg Depression Rating Scale (MADRS);
- d) Documented (i.e., chart review) lifetime failure to respond to ≥ 3 adequate dose/duration antidepressant treatment trials, ≥ 1 medication failure in the current depressive episode;
- e) Good command of the English language.

Exclusion Criteria

- a) Meets criteria for any DSM-IV diagnosis for schizophrenia, bipolar, schizoaffective, obsessive-compulsive, personality, or panic disorders;
- b) Any recent (within past 12 months) history of substance dependence or abuse (except tobacco), determined by reported history or urine drug screen;
- c) Ability to become pregnant and not using effective contraception;
- d) Contraindication against the use of nitrous oxide:
 - 1) Pneumothorax
 - 2) Bowel obstruction
 - 3) Middle ear occlusion
 - 4) Elevated intracranial pressure
 - 5) Chronic cobalamin and/or folate deficiency treated with folic acid or vitamin B12
 - 6) Pregnant patients
 - 7) Breastfeeding women
- e) Inability to provide informed consent;
- f) Any other factor that in the investigators' judgment may affect patient safety or compliance.

5. Enrollment

Participants will be recruited in part through the Volunteer for Health registry at Washington University School of Medicine and the Washington University TRMD Database (120+ individuals with TRMD carefully screened over the past 8 years, maintained by [name]; IRB# 201102247). Eligible and interested participants will be consented for participation and enrolled in the study by study personnel. We will recruit a total of 40 participants currently in an episode of major depressive disorder, medication-free or on psychotropic medications. To complete the study, we will enroll up to 40 participants to achieve adequate sample size.

6. Methods

6.1. Study Design

This is a double-blind, randomized placebo-controlled crossover trial in which all subjects will undergo three randomized, one hour N₂O inhalation sessions each separated by at least 4 weeks. Inhalations will include exposure to placebo (0% N₂O), 25% N₂O (low dose), and 50% N₂O (high dose). Mood will be assessed at baseline (immediate pre-treatment), immediate (1 hour post-inhalation), sustained (24 hours) and at one and two weeks, and one month. We will also assess for potential psychiatric side effects including psychosis and disassociation.

There will be up to 14 study visits involved with participation. The screening visit (Visit 1) will be used to verify eligibility and collect background information.

Specifically, we will collect patient demographic information, medical history, vital signs and a research team member will perform a physical exam. A urine sample will be collected for drug, and an optional blood draw may be collected if the study physician requests tests to confirm participants' safety to participate. Psychiatric assessments (completed by the participant and administered by the research team) will be performed to assess for major depression, other mental health diagnoses including significant anxiety disorder, post-traumatic stress disorder, and psychosis or dissociation.

Visit 2 may directly follow Visit 1 on the same day, if needed. Visit 2 (Baseline visit) will ask participants to fill out several mood-based questionnaires, pass a urine pregnancy screen (Baseline visit only), receive a total of 60 minutes gas inhalation, and after the observation period, will be asked several mood-based questionnaires again. Visit 3 is scheduled approximately 22-28 hours after completion of the inhalation session, and participants will have vital signs taken and mood questionnaires asked. Visits 4 and 5 will occur 1 and 2 week(s), respectively, after inhalation session one, and involve asking participants about their mood and mental state. Visit 6 will occur 4 weeks after inhalation session one, and will include questionnaires to account for a 4 week follow up and also a baseline visit for the next gas concentration. The procedures for Visit 6 will be identical to Visit 2 (besides urine pregnancy screen) with gas inhalation and mood-based questionnaires before and 1 hour after inhalation. The remaining follow up visits will follow the same outline until all 3 gas concentrations have been given to each participant and follow up visits 24 hours, and 1, 2, and 4 weeks after each inhalation session have been completed. If necessary, the 1, 2, and 4 week post inhalation session visits may be conducted over the phone with Principal Investigator approval.

Participants will be monitored after each inhalation session before being allowed to leave. Optional labs may be ordered by the screening physician to confirm the safety of a patient. These screening labs might include but are not limited to a comprehensive blood panel and a complete blood count.

Patients will be reimbursed with \$5 + parking for each visit completed after the Screening Visit for their expenses and time commitment. If a participant completes all visits they will receive \$65. Otherwise if the participant ends participation before the study visits are complete, the participant will be compensated \$5 for each visit they did complete.

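### A pregnancy test is required only before the first of three inhalations, although pregnancy is a listed contraindication to nitrous oxide

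*Combined protocol and SAP*

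**What the plan says.** Section 6.1 (Study Design) sets out the visits. At Visit 2, before the first inhalation, participants must "pass a urine pregnancy screen (Baseline visit only"). For the second inhalation it states: "The procedures for Visit 6 will be identical to Visit 2 (besides urine pregnancy screen"). For the rest of the schedule it states: "The remaining follow up visits will follow the same outline until all 3 gas concentrations have been given to each participant".

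The Exclusion Criteria, which follow Section 4.1, contain two relevant items. Item c excludes anyone with "Ability to become pregnant and not using effective contraception". Item d is headed "Contraindication against the use of nitrous oxide" and includes "6) Pregnant patients".

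On other tests, Section 6.1 says "Optional labs may be ordered by the screening physician to confirm the safety of a patient". The examples given are blood tests, and a pregnancy test is not named. The urine sample at the screening visit is for drug testing.

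**The concern.** Pregnancy is a contraindication that can arise between doses. The protocol tests for it before the first dose and then does not require another test, although two more doses follow over at least 8 weeks. A participant who conceives after session 1 could be given 25% or 50% nitrous oxide with every stated procedure followed, because nothing in the text requires the pregnancy to be detected first.

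The protocol also does not treat contraception alone as enough before session 1: it requires effective contraception at entry and still tests at Visit 2. It gives no reason why contraception should suffice before sessions 2 and 3. What is at stake is patient safety. The analysis is affected only slightly, and only by the remedy.

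**Working it through.** The plan states no figure on this point, so there is none to reproduce. The check has four steps.

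**1. Where a pregnancy test is required.**

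| Inhalation | Visit text (Section 6.1) | Test required? | Minimum age of the only required test |
|---|---|---|---|
| 1 | Visit 2, test stated | Yes | same visit |
| 2 | Visit 6, test expressly excepted | No | 4 weeks |
| 3 | Same outline as before | No, by inference | 4 + 4 = 8 weeks |

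The ages use the minimum gap of 4 weeks between sessions (Synopsis and Section 6.1). Section 6.1 also calls Visit 6 a baseline visit for the next gas, so the limit to the baseline visit might be read as covering every pre-dose baseline. The explicit exception for Visit 6 rules that out for session 2.

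**2. Whether a check could sit at another visit.** The schedule is screening, then three blocks of four visits (session, 24 hours, 1 week, 2 weeks), then a final 4-week visit: 1 + 3 × 4 + 1 = 14. Payment is 13 × $5 = $65. Both match Section 6.1, so no visit is unaccounted for, and none of those described after Visit 2 includes a pregnancy test.

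**3. How many later inhalations are active.** Each participant receives placebo (P), 25% (L) and 50% (H), in an order drawn at random (Section 6.2). The six possible orders are:

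| Order | Session 2 active? | Active inhalations in sessions 2 and 3 |
|---|---|---|
| P, L, H | yes | 2 |
| P, H, L | yes | 2 |
| L, P, H | no | 1 |
| H, P, L | no | 1 |
| L, H, P | yes | 1 |
| H, L, P | yes | 1 |

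Section 6.1 allows for early stopping ("Otherwise if the participant ends participation before the study visits are complete"), so the count depends on the sessions received:

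- One session: no inhalation without a required test.
- Two sessions: one, active in 4 of 6 orders and placebo in 2 of 6.
- Three sessions: two. Both are active in 2 of 6 orders and exactly one in 4 of 6, so at least one is always active.

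**4. Cost of testing before every session.**

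- Extra tests: at most 2 per participant able to become pregnant. The upper bound is 2 × 40 = 80, if all 40 were such participants and all reached session 3.
- Periods lost after a positive test: 2 if found before session 2, 1 if found before session 3. Of 40 × 3 = 120 planned periods, that is 2/120 = 1.7% or 1/120 = 0.8%. On the 24 patients in the Power Analysis (24 × 3 = 72 periods) it is 2/72 = 2.8% or 1/72 = 1.4%.

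**The case against.** The strongest reply is that this is a deliberate rule with other controls around it. The two parenthetical limits show that the authors thought about repeat testing and declined it. Anyone able to become pregnant must be using effective contraception at entry. Investigators may exclude for any safety reason, an attending-level anesthesiologist supervises each inhalation, and participants are contacted at 24 hours and at 1, 2 and 4 weeks, when a known pregnancy could be reported. The residual gap is an unrecognised pregnancy despite contraception, in a trial open to both sexes and ages 18 to 75. The standard operating procedures cover subject management (Section 8.1). Neither they nor the consent pages were available for review, and either could hold instructions on contraception or pregnancy reporting. For session 3 the omission is inferred, not stated.

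Much of this stands. The rule is a stated choice and not a contradiction, the risk is probably low, and nothing can be said about how sites act in practice. But none of these provisions is a required check. The exclusions are eligibility criteria with no re-check described. The optional labs are described as screening labs. The monitoring under supervision (ECG, oximetry, blood pressure, end-tidal CO₂) does not detect pregnancy. The follow-up contacts are not said to ask about it. The objections bear on how serious the gap is and leave its existence untouched.

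**Conclusion.** The concern holds. As written, the protocol allows a participant able to become pregnant to receive up to two inhalations after the only required pregnancy test. If all three sessions are completed, at least one of the two is active nitrous oxide.

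These counts are exposures without a required check and do not measure expected harm. The documents give no number of participants able to become pregnant, no pregnancy probability and no estimate of fetal risk. The conclusion rests on two readings: that the third session follows the same outline as the second, and that no document outside the protocol adds a test. Even if an operating procedure did add one, the protocol text would still exempt Visit 6 and should be brought into line. This is a cheap safety improvement that should be made; confidence in its importance is moderate.

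**What to change.** In Section 6.1, delete the parenthetical that limits the test to the baseline visit and the one that exempts Visit 6 from it. Add:

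*Participants able to become pregnant must have a negative urine pregnancy test before each of the three inhalation sessions. No further inhalation is given after a positive test.*

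The test is already in the protocol, and the added tests fall at visits attended in person for dosing. The sample size, blinding and analysis model need no change.

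A positive test leaves missing crossover periods, and counting periods slightly understates that loss. A participant stopped before session 2 contributes no within-person comparison of 25% with 50%. One stopped before session 3 contributes none in 4 of the 6 orders, since only L, H, P and H, L, P give both doses in the first two sessions. This is a small price for not dosing against a listed contraindication.
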